**CRAD001JUS228T**

**Study Principal Investigator:**

[name].  
Associate Professor of Medicine  
Section of Medical Oncology  
Sidney Kimmel Cancer Center  
Thomas Jefferson University  
Email: [contact]

Title of Trial:	A phase II clinical trial evaluating neoadjuvant endocrine therapy with everolimus in postmenopausal women with hormone receptor positive/HER 2negative breast cancers with low and intermediate risk ( $\leq 25$ ) Oncotype Dx Recurrence Scores	
Protocol Number:	CRAD001JUS228T	
Sponsor:	Thomas Jefferson University	
Trial Duration:	24 months	Phase of Trial: II
Trial Centers:	Thomas Jefferson University: Sidney Kimmel Cancer Cener Yale University: Smilow Cancer Hospital-Main Campus, Smilow Hospital Care Centers	
Patient Population	This study will enroll postmenopausal women with hormone receptor positive/HER-2 negative Stage II-III breast cancer with low to intermediate risk ( $\leq 25$ ) Oncotype Dx Recurrence Scores, who have not had surgical resection of their breast cancer.	
Objectives:	
Primary objectives
 
 
The primary objective of the study is to determine the percent of postmenopausal patients with stage II-III hormone receptor positive/ HER2 negative breast cancers and an Oncotype Dx recurrence score <math>\leq 25</math>, who achieve a PEPI score of 0 following neoadjuvant treatment with everolimus and an aromatase inhibitor
 
 
Secondary objectives
 
 
To assess the tolerability and side effect profile of neoadjuvant aromatase inhibitor therapy and everolimus
 
To identify biologic markers predictive of clinical and pathologic response (pathologic complete response or PEPI 0) to neoadjuvant aromatase inhibitor therapy and everolimus in postmenopausal hormone receptor positive/HER2 negative breast cancer patients selected by Oncotype Dx Recurrence Score <math>\leq 25</math>, on tissue biopsies obtained at baseline and at end of treatment
 
	
Number of Patients:	Up to 33 patients will be enrolled on the clinical trial.	
Trial Design:	This is an open label, non-randomized phase II clinical trial evaluating the efficacy and safety of neoadjuvant endocrine therapy with everolimus in postmenopausal women with hormone receptor positive/HER2 negative breast cancers with low and intermediate risk ( $\leq 25$ ) Oncotype Dx Recurrence Scores	
Trial Drug(s), Dose, and Mode of Administration	Eligible patients will receive daily aromatase inhibitor therapy (anastrozole 1 mg, or letrozole 2.5 mg or exemestane 25 mg) in combination with everolimus 10 mg daily. Both study agents will be administered orally for a total of 26 weeks.	

Inclusion Criteria:	

1. Patients must have a histologically confirmed diagnosis of hormone receptor positive, HER2 negative invasive breast carcinoma.

2. Tumors must be estrogen and/or progesterone receptor positive according to ASCO/CAP 2010 guidelines as either ER or PR <math>\geq 1\%</math> positive nuclear staining by immunohistochemistry. Estrogen and/or progesterone receptor results by Oncotype Dx will not be accepted.

3. Tumors must be HER2 negative as defined according to ASCO/CAP 2013, as HER2 0 – 1+ by IHC or non-amplified FISH or CISH. If HER2 IHC is 2+, FISH/CISH must be performed and must not be positive (must be a ratio of <math>< 2</math>), but otherwise FISH/CISH is not required if IHC is 0 or 1+ by institutional standards.

4. Patients must not have had prior ipsilateral breast-conserving surgery or total mastectomy and be eligible for neoadjuvant treatment.

5. Clinical Stage II-IIIC (T2-4 N0-3 M0) by mammogram, ultrasound or MRI

6. Baseline Oncotype Dx recurrence score <math>\leq 25</math>.

7. Staging studies with a CT scan of the chest and abdomen and bone scan, or a PET/CT is required for clinical stage III, and are considered optional for stage II breast cancers.

8. Patients with multifocal, multicentric and synchronous bilateral breast cancers are allowed:

• Multifocal disease is defined as more than one invasive cancer <math>< 2</math> cm from the largest lesion within the same breast quadrant.

• Multicentric disease is defined as more than one invasive cancer <math>\geq 2</math> cm from the largest lesion within the same breast quadrant or more than one lesion in different quadrants.

• Synchronous bilateral disease is defined as invasive breast cancer in both breasts, diagnosed within 30 days of each other.

• In patients with multicentric or bilateral invasive breast cancers, all sampled lesions must be hormone receptor-positive and HER2-negative. Any lesion measuring <math>\geq 1</math> cm must have an Oncotype Dx and the score must be <math>\leq 25</math>. Lesions less than 1 cm in size are not required to have an Oncotype Dx. One lesion (typically the largest) should be designated as the target lesion for which clinical and radiographic response to the neoadjuvant therapy will be judged.

• Patients with a hormone receptor-positive, HER2-negative invasive cancer that meets study criteria may have ductal carcinoma in situ in another quadrant of the same breast or in the contralateral breast even if the DCIS is hormone receptor-negative.

9. Patients must have adequate bone marrow function, as defined by peripheral granulocyte count of <math>\geq 1,500/\text{mL}</math>, hemoglobin <math>\geq 9 \text{ g/dL}</math> and a platelet count <math>\geq 100,000/\text{mL}</math> within 28 days prior to registration.

10. Patients must have adequate hepatic function obtained within 28 days prior to registration and documented by all of the following:

• Bilirubin <math>\leq 1.5 \text{ mg/dL}</math> (or <math>\leq 3.0 \text{ mg/dL}</math> if due to Gilbert's Syndrome)

• ALT and AST <math>\leq 1.5 \times</math> Institutional Upper Limit of Normal (IULN)

----------------------------	---

	

• Alkaline phosphatase <math>\leq 1.5 \times</math> IULN

 
11. Patients must have adequate renal function with serum creatinine level <math>\leq</math> IULN within 28 days prior to registration.
 
12. Patients must have a fasting cholesterol <math>\leq 300</math> mg/dl OR <math>\leq 7.75</math> mmol/L and triglycerides <math>\leq 2.5 \times</math> IULN obtained within 28 days prior to registration. Patients may be on lipid lowering agents to reach these values.
 
13. Patients must have a ECOG performance status of 0-2.
 
14. Patients must be able to take oral medications.
 
15. Postmenopausal women (women are considered post-menopausal and not of child-bearing potential if they are <math>> 18</math> years of age and have had 12 months of natural (spontaneous) amenorrhea with an appropriate clinical profile (e.g. age appropriate, history of vasomotor symptoms or biochemically postmenopausal by estradiol and FSH levels) prior to enrollment, or have had surgical bilateral oophorectomy (with or without hysterectomy) prior to registration. Medical ovarian suppression with LHRH agonists to render a patient postmenopausal will not be acceptable.
 
16. Patients or their legally authorized representative must be informed of the investigational nature of this study and must sign and give written informed consent prior to any screening procedures in accordance with institutional and federal guidelines.

Exclusion Criteria:	

1. Patients must not have inflammatory breast cancer (T4d) and must not have metastatic breast cancer (Stage IV disease).

2. Patients must not have prior exposure to mTOR inhibitors (e.g. rapamycin, everolimus, sirolimus, temsirolimus, deforolimus).

3. Patients must not have prior treatment with any investigational drug within the preceding 28 days and must not be planning to receive any other investigational drug for the duration of the study.

4. Patient may not have any impairment of gastrointestinal function or gastrointestinal disease that may significantly alter the absorption of the drug (e.g. ulcerative disease, uncontrolled nausea, vomiting, diarrhea, malabsorption syndrome or small bowel resection).

5. Uncontrolled diabetes mellitus as defined by HbA1c <math>>8\%</math> within 28 days prior to registration despite adequate therapy.

6. Patients who have any severe and/or uncontrolled cardiac disease within <math>\leq 6</math> months prior to start of everolimus, including: unstable angina pectoris, Symptomatic congestive heart failure of New York heart Association Class III or IV, myocardial infarction, serious uncontrolled cardiac arrhythmia, or any other clinically significant cardiac disease

7. Patients must not have an organ allograft or other history of immune compromise.

8. Patients must not be receiving chronic, systemic treatment with corticosteroids or other immunosuppressive agent. Topical or inhaled corticosteroids are allowed.

9. Patients must not have a known history of HIV seropositivity

	
10. Patients must not have a known diagnosis of hepatitis B or C. Patients with the following risk factors must have hepatitis screening pre-treatment:
 

• Blood transfusions prior to 1990

• Current or prior IV drug users

• Current or prior dialysis

• Household contact with a hepatitis B or C patient

• Current or prior high-risk sexual activity

• History of jaundice.

 
11. Patients must not have any known uncontrolled underlying pulmonary disease or severely impaired lung function (spirometry and DLCO 50% or less of normal and O2 saturation 88% or less at rest on room air),
 
12. Active (acute or chronic) or uncontrolled severe infection.
 
13. Patients who have received live attenuated vaccines within 1 week of start of Everolimus, or have plans to receive such vaccination while on protocol treatment. Patient should also avoid close contact with others who have received live attenuated vaccines. Examples of live attenuated vaccines include intranasal influenza, measles, mumps, rubella, oral polio, BCG, yellow fever, varicella and TY21a typhoid vaccines;
 
14. , Patients who are currently part of or have participated in any clinical investigation with an investigational drug within 1 month prior to dosing;
 
15. Patients must not have taken within 14 days prior to registration , be taking, nor plan to take while on protocol treatment, strong CYP3A4 inhibitors, and/or CYP3A4 inducers.
 
16. Patients with active bleeding diathesis.

Statistical Methodology:	This is a single arm phase II study to evaluate neoadjuvant endocrine therapy with everolimus in postmenopausal women with hormone receptor positive/HER2 negative breast cancers with low and intermediate risk ( $\leq 25$ ) Oncotype Dx recurrence score. The primary endpoint is response defined as a PEPI-0 rate. A treatment with minimal activity would be expected to have PEPI-0 rate of 25%. Alternatively, a treatment will be considered worthy of further study if its true PEPI-0 rate is 45% or better. Simon's optimal two-stage design is employed for this single-arm phase II trial. The sample size is 27. Assuming 10-20% ineligibility rate, we plan to enroll up to 33 patients totally.

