## 4.2 Exclusion criteria

1. Patients must not have inflammatory breast cancer (T4d) and must not have metastatic breast cancer (Stage IV disease).
2. Patients must not have prior exposure to mTOR inhibitors (e.g. rapamycin, everolimus, sirolimus, temsirolimus, deforolimus).
3. Patients must not have prior treatment with any investigational drug within the preceding 28 days and must not be planning to receive any other investigational drug for the duration of the study.
4. Patient may not have any impairment of gastrointestinal function or gastrointestinal disease that may significantly alter the absorption of the drug (e.g. ulcerative disease, uncontrolled nausea, vomiting, diarrhea, malabsorption syndrome or small bowel resection).
5. Uncontrolled diabetes mellitus as defined by HbA1c >8% within 28 days prior to registration despite adequate therapy.
6. Patients who have any severe and/or uncontrolled cardiac disease within  $\leq 6$  months prior to start of Everolimus, including: unstable angina pectoris, Symptomatic congestive heart failure of New York heart Association Class III or IV, myocardial infarction, serious uncontrolled cardiac arrhythmia, or any other clinically significant cardiac disease
7. Patients must not have an organ allograft or other history of immune compromise.
8. Patients must not be receiving chronic, systemic treatment with corticosteroids or other immunosuppressive agent. Topical or inhaled corticosteroids are allowed.
9. Patients must not have a known history of HIV seropositivity
10. Patients must not have a known diagnosis of hepatitis B or C. Patients with the following risk factors must have hepatitis screening pre-treatment:
  - Blood transfusions prior to 1990

- Current or prior IV drug users
- Current or prior dialysis
- Household contact with a hepatitis B or C patient
- Current or prior high-risk sexual activity
- History of jaundice.

11. Patients must not have any known uncontrolled underlying pulmonary disease or severely impaired lung function (spirometry and DLCO 50% or less of normal and O2 saturation 88% or less at rest on room air),

12. Active (acute or chronic) or uncontrolled severe infection.

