Very common - Pneumonitis, epistaxis, cough

Common - Dyspnea

Uncommon - Hemoptysis, pulmonary embolism

Rare - Acute respiratory distress syndrome

*Gastrointestinal disorders*

Very common - Stomatitis, diarrhea, nausea

Common - Vomiting, dry mouth, abdominal pain, oral pain, dyspepsia, dysphagia

*Skin and subcutaneous tissue disorders*

Very common - Rash, pruritus

Common - Dry skin, nail disorder, acne, erythema, hand-foot syndrome

Rare - Angioedema

*Musculoskeletal and connective tissue disorders*

Common - Arthralgia

*Renal and urinary disorders*

Common - Proteinuria, renal failure  
Uncommon - Increased daytime urination, acute renal failure

*Reproductive system and breast disorders*

Common - Menstruation irregular  
Uncommon - Amenorrhea

*General disorders and administration site conditions*

Very common - Fatigue, asthenia, edema peripheral  
Common - Pyrexia, mucosal inflammation  
Uncommon - Non-cardiac chest pain, impaired wound healing

*Investigations*

Very common - Weight decreased  
Common blood - Alanine aminotransferase increased, aspartate aminotransferase increased, creatinine increased

a Includes all reactions within the 'infections and infestations' system organ class including common: pneumonia, urinary tract infection

and uncommon: bronchitis, herpes zoster, sepsis, abscess, and isolated cases of opportunistic infections (e.g. aspergillosis, and rare: viral myocarditis, candidiasis and hepatitis B)

b Includes different bleeding events from different sites not listed individually

c Includes very common: pneumonitis and common: interstitial lung disease, lung infiltration, alveolitis, pulmonary

alveolar hemorrhage, and pulmonary toxicity

d Includes very common: stomatitis; common: aphthous stomatitis, mouth and tongue ulceration; uncommon:

glossitis, glossodynia

e reported as palmar-plantar erythrodysesthesia syndrome

2. Pregnancy and Lactation: Pregnancy category D. It is not known if everolimus is excreted in human milk.

3. Drug Interactions: Everolimus is metabolized by CYP3A4 in the liver and to some extent the intestinal wall. Due to the extensive number of everolimus drug interactions, a complete patient medication list, including everolimus, should be screened prior to initiation of everolimus.

Drug	Severity	Recommendation
Strong CYP3A4 inhibitor or P-glycoprotein (PgP) inhibitor	Major	Co-administration should be avoided

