### 7.3.4 Management of non-infectious pneumonitis

Non-infectious pneumonitis is a class effect of rapamycin derivatives. Cases of non-infectious pneumonitis (including interstitial lung disease) have also been described in patients taking Everolimus. Some of these have been severe and on rare occasions, a fatal outcome was observed.

- A diagnosis of non-infectious pneumonitis should be considered in patients presenting with non-specific respiratory signs and symptoms such as hypoxia, pleural effusion, cough or dyspnea, and in whom infectious, neoplastic and other non-medicinal causes have been

excluded by means of appropriate investigations. Patients should be advised to report promptly any new or worsening respiratory symptoms.

If non-infectious pneumonitis develops, the guidelines in Table 0 should be followed. Consultation with a pulmonologist is recommended for any case of pneumonitis that develops during the study.

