**Table 0 Management of non-infectious pneumonitis**

Grading of Pneumonitis:

Grade 1 (Asymptomatic, radiographic findings only)

Grade 2 (Symptomatic, not interfering with Activities of Daily Living)

Grade 3 (Symptomatic, Interfering with Activities of Daily Living. O2 indicated)

Grade 4 (Life-threatening, ventilatory support indicated)

Worst grade pneumonitis	Suggested investigations	Management of pneumonitis	Everolimus dose adjustment
Grade 1	CT scans with lung windows.	No specific therapy is required	No dose adjustment required. Initiate appropriate monitoring.
Grade 2	CT scan with lung windows. Consider pulmonary function testing includes: spirometry, DLCO, and room air O 2 saturation at rest. Consider a bronchoscopy with biopsy and/or BAL. Monitoring at each visit until return to ≤ grade 1. Return to initial monitoring frequency if no recurrence.	Symptomatic only. Consider corticosteroids and/or other supportive therapy if symptoms are troublesome.	Rule out infection and consider interruption of Everolimus until symptoms improve to Grade ≤ 1. Re-initiate Everolimus at one dose level lower. Discontinue Everolimus if failure to recover within ≤ 28 days.
Grade 3	CT scan with lung windows and pulmonary function testing includes: spirometry, DLCO, and room air O 2 saturation at rest. Monitoring at each visit until return to ≤ grade 1. Return to initial monitoring frequency if no recurrence. Bronchoscopy with biopsy and/or BAL is recommended.	Consider corticosteroids if infective origin is ruled out. Taper as medically indicated.	Rule out infection and interrupt Everolimus until symptoms improve to Grade ≤ 1. Consider re-initiating Everolimus at one dose level lower (approximately 50% lower than the dose previously administered depending on individual clinical circumstances) Discontinue Everolimus if failure to recover within ≤ 28 days., or toxicity recurs at grade 3.
Grade 4	CT scan with lung windows and required pulmonary function testing, if possible, includes: spirometry, DLCO, and room air O 2 saturation at rest. Monitoring at each visit until return to ≤ grade 1. Return to initial monitoring frequency if no recurrence. Bronchoscopy with biopsy and/or BAL is recommended if possible.	Consider corticosteroids if infective origin is ruled out. Taper as medically indicated.	Rule out infection and discontinue Everolimus.

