## 9 VISIT SCHEDULE AND ASSESSMENTS

### 9.1 Baseline assessment

The following baseline assessments have to be performed at any time prior to initiation of treatment and must include:

- Determination of Oncotype Dx recurrence score.
- Determination of tumor HER2, ER and PR status

The following baseline assessments have to be performed within 4 weeks prior to initiation of treatment and must include:

- Complete history and review of systems including assessment of Eastern Cooperative Oncology Group Performance Status (ECOG) performance status,

review of concomitant medication and documentation of the date of the last dose of endocrine or chemotherapy received before entering the study.

- Complete physical examination including measurements of height, weight, and vital signs including oxygen saturation by pulse oximetry.
- Record breast tumor and axillary node measurements by physical exam for palpable tumors.
- Bilateral mammogram with clip placement to mark tumor bed
- MRI of the involved breast (or a unilateral ultrasound of the involved breast if a patient is unable to have a breast MRI due to claustrophobia, metal in body, or lack of insurance coverage, etc).
- If suspicious lymph nodes are detected clinically or by imaging, a diagnostic image guided fine needle aspiration or biopsy of the suspicious node is required.
- Complete blood count (CBC) including platelets and differential
- Comprehensive metabolic profile (CMP) including albumin, calcium, phosphorus, BUN, creatinine, total bilirubin, alkaline phosphatase, LDH, AST, ALT, Na, K, Cl, CO2 and fasting glucose.
- Fasting lipid profile
- Hemoglobin A1C
- PTT, PT and INR
- 12-lead ECG
- Complete microscopic urine analysis.
- CT scan of the chest and abdomen for clinical stage III or symptomatic stages II
- Bone scan for clinical stage III or symptomatic stage II.
- Bone density assessment ( within 12 months). If results of baseline bone density confirm evidence of osteoporosis, treatment for osteoporosis will be left to the discretion of the treating physician.

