## 9.2 Evaluation During Study

The following assessments will be performed every 4 weeks ( +/- 3 days) except as noted:

- Medical history including ECOG performance status, treatment related AE assessment, concomitant medication review and study drug compliance assessment including dose and any treatment interruption.
- Physical examination including measurements of weight and vital signs including oxygen saturation by pulse oximetry.

- Record breast tumor and axillary node measurements by physical exam for palpable tumors.
- CBC, including differential and platelets
- CMP including albumin, calcium, phosphorus, BUN, creatinine, total bilirubin, alkaline phosphatase, LDH, AST, ALT, Na, K, Cl, CO2 and fasting glucose.
- PTT,PT and INR
- Radiological Assesment: The involved breast, and axilla (in patients with enlarged axillary nodes at baseline), will be reimaged by MRI between weeks 12 and 13 and again after completing neoadjuvant therapy. If a patient is unable to have a breast MRI (due to claustrophobia, metal in body, or lack of insurance coverage, etc) a breast ultrasound will be used to replace MRI at baseline, at 12-13 weeks and after completing neoadjuvant therapy. Other imaging, such as ultrasonography or MRI, is at the discretion of the treating physicians.
- Breast imaging may be repeated any time during therapy if clinical suspicion of progression of disease.
- Dispense study medication in appropriate supply
- Accountability and compliance check of returned pill diary and study medication
- Fasting lipid profile every 2 cycles ( every 8 weeks)

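### As written, the lung-function part of exclusion 11 is not triggered by a resting room-air oxygen saturation of 88% or less alone, though saturation is the only one of its three measures in the 9.1 baseline list

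*Combined protocol and SAP*

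**What the plan says.** Exclusion 11 appears with the same wording in the synopsis and in section 4.2. It gives two routes to exclusion, separated by *or*. The first is pulmonary disease that is known and uncontrolled. The second is "severely impaired lung function (spirometry and DLCO 50% or less of normal and O2 saturation 88% or less at rest on room air". Within the second route, spirometry, DLCO and saturation are joined by *and* at both joins.

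Section 9.1 lists the assessments required in the 4 weeks before treatment. The only one of the three measures it includes is oximetry, as part of the physical examination: "vital signs including oxygen saturation by pulse oximetry". Spirometry and DLCO are not listed.

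In the text available, those two tests appear outside exclusion 11 only in Table 0, for working up pneumonitis of grade 2 or above once it has occurred. The grade 2 row, for example, reads "Consider pulmonary function testing includes: spirometry, DLCO, and room air".

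On the risk itself, section 6.1.1 lists "Very common - Pneumonitis, epistaxis, cough". The section on managing non-infectious pneumonitis says of reported cases: "Some of these have been severe and on rare occasions, a fatal outcome was observed".

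**The concern.** A numeric limit in an eligibility criterion lets two centres make the same decision from the same reading. Here the one reading that every patient will have cannot produce that decision under the part of the criterion that contains the limit. A site that follows the words exactly would record a saturation of 88% or less and still find that the lung-function route does not apply.

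Oxygenation also matters during treatment. The protocol asks investigators to suspect pneumonitis in patients with "non-specific respiratory signs and symptoms such as hypoxia, pleural effusion, cough or dyspnea". Oximetry is repeated every 4 weeks under section 9.2 ("Physical examination including measurements of weight and vital signs including oxygen saturation by pulse oximetry"), and resting room-air saturation is part of the work-up in Table 0. A patient who starts at 88% or less already has a low value on that measure, so a low value on treatment would be harder to interpret. That last step is an inference; the protocol does not state it.

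**Working it through.** The protocol gives no figure to reproduce here. The check compares the logic of the criterion with the list of baseline tests.

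**Inputs**
- Measures named in the lung-function route of exclusion 11 (synopsis and 4.2): spirometry, DLCO, and resting room-air saturation, so 3.
- Of these, measures in the 9.1 baseline list: saturation only, so 1.
- Measures not requested at baseline: 3 − 1 = 2 (spirometry and DLCO).

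**Rules**
- Let S mean spirometry at 50% of normal or less, D mean DLCO at 50% of normal or less, and O mean resting room-air saturation at 88% or less.
- Literal rule: S and D and O.
- Rule with the second connector changed to *and/or*: (S and D) or O.

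| Patient | Literal rule | Changed rule |
|---|---|---|
| O true; spirometry and DLCO not done | not met | met |
| O true; S or D known to be false | not met | met |
| O true; S and D both true | met | met |
| O false; S and D both true | not met | met |
| O false; spirometry and DLCO not done | not met | not met |

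The first row is what the 9.1 list alone produces for a patient with low saturation. Under the literal rule the route needs 2 further results; under the changed rule it needs none. The fourth row shows a second effect of the change: two low lung-function results would exclude even with a saturation above 88%.

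**Does the protocol use *and* loosely elsewhere?** Where it intends alternatives, it usually marks them. Inclusion 2 uses *and/or* for the receptors, exclusion 15 uses *and/or* for the CYP3A4 drugs, inclusion 12 uses a capitalised *OR* between cholesterol units, and exclusion 11 itself uses *or* between its two routes. A site that reads *and* as *and* therefore has support in the text. Nothing in the protocol says that one limit is enough.

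**Could another criterion catch the patient in the first row?** The other route of exclusion 11 needs disease that is known and uncontrolled. Exclusion 6 covers cardiac disease, including "or any other clinically significant cardiac disease". Exclusion 12 covers active or severe infection. Inclusion 4 requires eligibility for neoadjuvant treatment. Each may apply, but only after the investigator attributes the low reading to a cause or decides that the patient is unfit. None refers to a saturation value.

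**The case against.** The strongest reply is that this is a matter of style. The clause is a parenthesis explaining what severe impairment means, and protocol prose often uses *and* to list indicators. The authors probably meant alternatives. That is likely, but it supports changing the connector, since the words say something else.

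The second reply is that such a patient would rarely be treated. The low reading is available before the first dose, the investigator may order lung tests or invoke another criterion, performance status must be 0 to 2, surgery is planned, and clinical stage III or symptomatic stage II calls for a baseline chest CT. This stands in large part and keeps the point small. The CT is a staging scan that does not cover asymptomatic stage II, and the other safeguards depend on clinical judgement.

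The third reply is that interpretation would hardly suffer. Section 9.1 records a baseline saturation for comparison, and pneumonitis is graded on symptoms, daily activities, and the need for oxygen or ventilation, with no saturation cut-off. This also largely stands, and the difficulty of interpretation is modest.

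The documents do not support several stronger readings:
- **That hypoxaemic patients will be enrolled.** The other criteria may exclude them, and no frequency of low saturation is given.
- **That poor baseline lung function raises the risk of pneumonitis.** The protocol says that pneumonitis is common and sometimes severe. It does not link it to baseline function.
- **That 9.1 is wrong to omit spirometry and DLCO, or to omit that oximetry is at rest on room air.** Routine lung testing is not shown to be needed, and the criterion already states the conditions of the reading.
- **That spirometry and DLCO are certainly called for nowhere else.** The upper rows of the study calendar are missing from the available text. The full 9.1 list and the calendar footnotes name neither test, so a hidden row is unlikely but cannot be ruled out.

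**Conclusion.** The point holds as a minor safety wording correction. Followed literally, exclusion 11 does not let a baseline resting room-air saturation of 88% or less exclude under its lung-function route, although that is the only one of the three measures in the 9.1 list. The remaining safeguards rest on judgement.

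The size can be stated only as a property of the rule: 1 of 3 measures is requested at baseline, and 2 more results are needed before the route applies. How many of the up to 33 enrolled patients this would touch is unknown and probably small. The design of 27 eligible patients, with 80% power at a one-sided level of 0.1, is unaffected.

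The conclusion assumes that sites apply the connectors as written and that the missing calendar rows do not add lung-function tests at baseline.

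**What to change.** In exclusion 11, in both the synopsis and section 4.2, replace the second connector (the one before the saturation limit) with *and/or*, leaving the limits as they are. Resting room-air saturation of 88% or less then excludes by itself.

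Add no baseline test. Add no clause that depends on whether earlier lung-function results exist, because eligibility would then turn on who happened to have been tested, and a time window would have to be defined. The retained spirometry and DLCO pair can be assessed only where those results are known, as is already the case.

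The cost is one connector changed in two places and possibly a few more exclusions. A patient with a saturation above 88% and no lung-function results is still not caught by this route.
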